### **Clinical Data Collection:**

The clinical information of hospitalized patients was collected through a medical record system and questionnaire survey, including chronic medical history, smoking history, chest HRCT imaging data, annual acute attack frequency, disease severity (BSI score), etc.

The information of health examiners is obtained through a survey questionnaire, including age, chronic medical history, smoking history, family history of tumors, and chest HRCT.

The imaging data were obtained from the Shanghai Shanghai pulmonary hospital. And all clinical data were extracted from the medical system by two individual researchers.

### **VOCs detection:**

On the HPPI-TOFMS detection platform, soft ionization was achieved by a commercial VUV-Kr lamp with a photon energy of 10.6 eV to predominantly produce radical cations ( $M^+$ ) which are formed as  $M + h\nu \rightarrow M^+ + e$ , which can ionize most VOCs in the breath sample. Meanwhile, some protonated ions are also produced. The VOCs with mass-charge ratio( $m/z$ ) in the range of [20, 320] were detected on HPPI-TOFMS. In this study, the area of the strongest peak in the range of  $[x-0.5, x+0.5]$  was calculated, normalized, and regarded as the feature of VOC with  $m/z$  of  $x$ . Thus, three hundred kinds of VOC ions features were extracted via breath detection in HPPI-TOFMS.

### **VOCs analysis:**

To select valuable breathomics features and avoid model over-fitting, a combined feature selection method was executed for breathomics features. Firstly, the breathomics features with no significant differences ( $p > 0.05$ ) between BE and controls were excluded. Then, the VOC ions with low intensity but highly correlated with other selected VOC ions (correlation coefficient  $> 0.9$ ) among all discovery samples were excluded. At last, a random forest (RF) model was constructed on the discovery data set, and the ten most important VOC ions were selected based on the feature coefficient in RF model.

In this study, we constructed BE detection models via six popular ML methods, Random Forests (RF), Logistic regression (LR), Xtreme Gradient Boosting (XGB), K-Nearest Neighbor (KNN), Decision tree (DT) and the soft ensemble algorithm of RF, XGB, and LR, in discovery data set. To evaluate the performance of VOCs based BE detection models, the model detection results were evaluated and compared with the HRCT confirmed diagnosis results in the blinded test set.

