### **Criteria:**

#### **Inclusion Criteria:**

Patients were recruited according to the following inclusion criteria: (1) Age>18 years; (2) the diagnosis of BE was according to European Respiratory Society guidelines for the management of adult bronchiectasis; (3) Willing to join in and sign the informed consent form. Healthy control subjects were recruited according to the following inclusion criteria:(1) Age>18 years; (2) No history of any lung disease (according to pulmonary imaging and physical examinations); (3) Willing to join in and sign the informed consent form.

Unhealthy control subjects were recruited according to the following inclusion criteria: (1) Age>18 years; (2) The diagnosis of ILD was according to HRCT and clinical symptoms by two experts' consensus; (3) The diagnosis of Sarcoidosis (SA) was according to American Thoracic Society Clinical Practice Guideline;(4) Willing to join in and sign the informed consent form.

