### **Statistical analysis**

In this study, descriptive statistics were described as frequencies (percentages) for categorical variables or medians (interquartile range [IQR]) for continuous variables. The Mann-Whitney U test for continuous variables and the chi-square test for categorical variables were calculated among the different groups. Sensitivity (SEN), specificity (SPE), and accuracy (ACC) were calculated to evaluate the BE detection performance. A receiver operating characteristic (ROC) curve was plotted, and the area under the ROC curve (AUC) was calculated to assess the overall performance of the VOCs based BE detection model. All statistical analyses were

performed by SAS version 9.4 (SAS Institute Inc., Cary, NC, USA) and the Origin software (version 2018). A p-value<0.05 was considered statistically significant. All tests were two tailed.

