## **Study plan**

### **To construct an easy, fast, and non-invasive VOCs-based bronchiectasis detection mode**

This study plans to recruit 200 Bronchiectasis patients diagnosed by HRCT from the Department of Respiratory and Critical Care Medicine of Shanghai Pulmonary Hospital and 200 healthy participants from July,2022 to March,2023.

The exhaled gas of admitted patients was collected on the day of admission, that of outpatients on the day of outpatient service, and that of examinees on the day of physical examination. After the exhaled gas was collected, VOCs were detected by mass spectrometry according to the standard processing flow, and the full spectrum of exhaled VOCs of Bronchiectasis patients and healthy people were analyzed to explore the characteristics of exhaled VOCs of Bronchiectasis patients and healthy people, Analyze the correlation between VOCs and clinical disease severity and prognosis (number of acute exacerbations) characteristics. The data of 400 cases were randomly assigned in a 5:2:3 ratio to the discovery cohort, internal validation, and blinded test cohorts. The discovery and internal validation sets were used for potential VOC biomarkers selection and diagnostic model construction.

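### No matching or adjustment for age or smoking is planned, so ions that track either can add to the test-set AUC and no planned analysis would separate them

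*Combined protocol and SAP*

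**What the plan says.** **Who is compared.** The healthy-control criterion begins "Healthy control subjects were recruited according to the following inclusion criteria:(1) Age>18 years", and the same age limit applies to patients. Inclusion Criteria and Exclusion Criteria contain no age band, matching rule or smoking rule. Under Study plan, 200 BE patients come from the respiratory department and 200 healthy participants are added. Breath is sampled from inpatients on admission, "that of outpatients on the day of outpatient service, and that of examinees on the day of physical examination".

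**How ions are chosen.** Under VOCs analysis, ions not differing significantly "between BE and controls were excluded". The survivors are pruned for correlation, and ten are kept by random forest importance. Age and smoking are not named as model inputs. The plan does not define controls at this step. I read them as the healthy participants, because the planned total is 200 + 200.

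**How performance is reported.** "The data of 400 cases were randomly assigned in a 5:2:3 ratio to the discovery cohort, internal validation, and blinded test cohorts". Statistical analysis lists sensitivity, specificity and accuracy, and states that "the area under the ROC curve (AUC) was calculated to assess the overall performance of the VOCs based BE detection model". No adjusted or stratified AUC and no age-and-smoking comparator is described.

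**What is recorded.** Clinical Data Collection lists smoking history for hospitalised patients and for examinees. It names age only for examinees (the patient list is open-ended) and does not mention outpatients.

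**The concern.** The two groups reach the study by different routes, and nothing in the plan aligns their age or smoking. If they differ, an ion that reflects age or tobacco exposure will differ between them without any link to bronchiectasis. The crude filter cannot tell such an ion from a disease marker.

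The study asks whether breath can detect bronchiectasis. An AUC built partly on age and smoking answers a different question, and both facts are available without a breath test. No planned result would show how much of the AUC came from that source.

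**Working it through.** **1. The plan's own figures.** 200 + 200 = 400. The 5:2:3 split gives 400 × 0.5 = 200, 400 × 0.2 = 80 and 400 × 0.3 = 120. If the groups divide evenly, the test set has 60 versus 60. The plan states no target AUC, effect size or power, so there is nothing further to reproduce.

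**2. Could anything planned deal with age or smoking?**
- Sampling controls (fasting, mouth rinse, diet and alcohol limits, ambient air check) do not bear on age or smoking balance.
- Excluding COPD, asthma, pneumonia and tumours may remove some smoking-related disease but balances neither factor.
- The test set is a random part of the same 400, so it guards against over-fitting and inherits any imbalance.
- "The Mann-Whitney U test for continuous variables and the chi-square test for categorical variables were calculated among the different groups": these tests could show an imbalance but do not alter the AUC.

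**3. What age or smoking alone could yield (assumed gaps).** For an age difference of *d* SD, AUC = Φ(*d*/√2): 0.57, 0.64, 0.71 and 0.76 at *d* = 0.25, 0.5, 0.8 and 1.0. For smoking, AUC = 0.5 + (p₁ − p₀)/2: 0.55 at 30% v 20%, 0.60 at 40% v 20%, 0.65 at 50% v 20%.

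**4. Passing the filter.** An ion with correlation ρ to age and no BE effect differs by ρ*d* SD. With 100 v 100 in discovery, SE = √(2/100) = 0.141, and the probability of passing is Φ(ρ*d*/0.141 − 1.96) + Φ(−ρ*d*/0.141 − 1.96). At ρ = 0.5 and *d* = 0.8, 0.40/0.141 = 2.83 and the result is 0.81. At *d* = 0, 0.25, 0.5 and 1.0 it is 0.05, 0.14, 0.42 and 0.94.

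**5. Simulation of the selection steps.** Assumptions:
- 300 independent normal ions: 15 correlated 0.3 with age (SD 12 years) and 15 shifted 1 SD by smoking; control smoking prevalence 20%.
- Selection by Mann-Whitney p ≤ 0.05, then the top ten by random forest importance. Correlation pruning is inactive because ion noise is independent.
- Random forest and logistic models only.
- BE signals: weak, 5 ions at 0.4 SD; moderate, 10 at 0.4 SD; strong, 10 at 0.6 SD; very strong, 10 at 0.8 SD.
- 150 replicates per scenario (200 for no signal with balance), each with 200 bootstrap samples. Monte Carlo SE is at most 0.007 for an AUC and about 0.04 for a rate.

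The adjusted AUC regresses the VOC score on age and smoking in test-set controls and compares the groups on residuals. Entries are random forest/logistic. Imbalance is years of age + percentage points of smoking.

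| BE signal | Imbalance | Crude AUC | Rise over balance | Adjusted AUC | Adjusted 95% CI above 0.5 |
|---|---|---|---|---|---|
| None | 0 | 0.50/0.50 | – | 0.50/0.50 | 2%/3% |
| None | 5+10 | 0.52/0.52 | +0.02/+0.02 | 0.50/0.51 | 3%/1% |
| None | 10+20 | 0.57/0.58 | +0.08/+0.09 | 0.51/0.51 | 3%/3% |
| None | 15+20 | 0.65/0.67 | +0.15/+0.17 | 0.51/0.50 | 1%/1% |
| Weak | 0 | 0.61/0.63 | – | 0.61/0.63 | 51%/69% |
| Weak | 5+10 | 0.61/0.64 | +0.01/+0.01 | 0.60/0.62 | 43%/59% |
| Weak | 10+20 | 0.65/0.67 | +0.04/+0.04 | 0.60/0.62 | 37%/51% |
| Weak | 15+20 | 0.69/0.71 | +0.08/+0.08 | 0.57/0.58 | 24%/26% |
| Moderate | 0 | 0.67/0.70 | – | 0.67/0.70 | 85%/89% |
| Moderate | 10+20 | 0.69/0.72 | +0.02/+0.02 | 0.66/0.69 | 71%/81% |
| Moderate | 15+20 | 0.71/0.74 | +0.04/+0.05 | 0.63/0.65 | 47%/53% |
| Strong | 0 | 0.83/0.87 | – | 0.83/0.87 | 100% |
| Strong | 10+20 | 0.83/0.87 | 0.00/0.00 | 0.83/0.86 | 100% |
| Strong | 15+20 | 0.83/0.87 | 0.00/0.00 | 0.80/0.83 | 99% |
| Very strong | 0 | 0.93/0.95 | – | 0.93/0.95 | 100% |
| Very strong | 15+20 | 0.93/0.95 | 0.00/0.00 | 0.92/0.94 | 100% |

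Rises were taken before rounding, so they may differ by 0.01 from the rounded columns. With no signal at 15+20, the crude AUC's 95% CI lay above 0.5 in 83–89% of runs. Two simpler versions (top ten ions by Mann-Whitney, linear or logistic score, 60 and 80 runs) gave 92% and 91%. At 15+20 the ten-ion panel held on average 6.5 age- or smoking-related ions with no signal, falling to 0.9 with a very strong one.

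**6. Check under other assumptions.** Here all ten ions are age- or smoking-related, with no BE effect and no selection step, and a linear classifier is used. Crude against adjusted AUC was 0.50 v 0.50 with balance; 0.58 v 0.50 at 0.5 SD of age and smoking 30% v 20%; 0.65 v 0.49 at 0.8 SD and 40% v 20%; and 0.73 v 0.51 at 1.0 SD, 40% v 20% and stronger ion links. The mechanism agrees; the size depends on the assumptions.

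**The case against.** **The harm is hypothetical.** No age or smoking distribution is given, and every simulation input (number of affected ions, correlations, smoking prevalence) is assumed. Only two of the six planned models were run. This stands: the figures show what could happen, not what did.

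**The effect is often small.** A modest imbalance adds 0.01–0.02, and a strong signal leaves no rise at any imbalance tested. A rise of 0.08 or more needs a weak or absent signal with the strong imbalance, or no signal with the middle one. This also stands, and it limits the weight of the point. It does not remove the point, because the plan cannot show which case applies.

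**The group tests would reveal an imbalance.** They might, but they leave its share of the AUC unknown.

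**A diagnostic AUC need not be adjusted, and the plan claims no independence from age and smoking.** True as to the claim. The crude AUC should stay; the adjusted one matters when readers take the result as evidence of a breath signature of the disease.

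**Adjustment does not fully recover the signal.** At 15+20 the weak-signal adjusted AUC is 0.57/0.58 against 0.61/0.63 under balance. Part of the likely reason is that affected ions have taken places in the panel, which later adjustment cannot give back. This stands as a limit of the remedy.

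**Disease controls are left out.** Participants with interstitial lung disease or sarcoidosis are defined as unhealthy controls. If they enter the filter, the contrast could differ from the one simulated. They lie outside the planned 200 + 200 and are not matched either.

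**Conclusion.** The concern holds. The plan neither balances nor adjusts for age or smoking at recruitment, ion selection, modelling or evaluation, and the held-out test set does not protect against this.

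Its size cannot be found from the documents. Over the assumed range, the rise in crude AUC runs from 0.00 (strong signal) to 0.15–0.17 (no signal, 15 years and 20 points). The case that matters most is a modest observed AUC, where a test with no disease signal could look informative. The documents do not say that the groups differ, so this is a gap in the plan, not a demonstrated bias. The change should be made; confidence is medium.

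**What to change.** 1. Tabulate age and smoking history by group in each of the three sets. Confirm that both are recorded for every patient, including outpatients, and name age explicitly among the patient data.
2. Keep the VOC models and the crude results. Beside the crude test-set AUC, report a covariate-adjusted AUC: regress the VOC score on age and smoking in test-set controls, compare cases and controls on the residuals, and give a bootstrap 95% CI with the regression refitted in each sample.
3. As a descriptive benchmark, give the test-set AUC of an age-plus-smoking model without VOCs, fitted outside the test set.
4. Claim detection independent of age and smoking only if the adjusted CI lies above 0.5. Otherwise report it as not shown, rather than absent.
5. Report any AUC gain over the benchmark as descriptive only, using scores from participants who played no part in building the model. The documents differ on who those are: VOCs analysis builds the models, including "the soft ensemble algorithm of RF, XGB, and LR, in discovery data set", whereas Study plan says "The discovery and internal validation sets were used for potential VOC biomarkers selection and diagnostic model construction".
6. If the test set is already open, label these analyses post hoc. The document is dated July 2023, after the planned end of recruitment in March 2023.

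**Cost.** No new samples and no model rebuild; outpatient age and smoking may have to be retrieved, and the headline may be less favourable.

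Precision is the main price. By Hanley–McNeil with 60 v 60, SE² = [A(1 − A) + 59(Q₁ − A²) + 59(Q₂ − A²)]/3600, where Q₁ = A/(2 − A) and Q₂ = 2A²/(1 + A). The crude 95% half-width (1.96 × SE) is 0.093, 0.080 and 0.057 at A = 0.7, 0.8 and 0.9. In the 15+20 runs the adjusted half-width was 0.13–0.14 with no or weak signal and 0.09–0.10 with a strong one. The rule in item 4 would miss a real weak signal in 74–76% of runs there, and in 31–49% even under balance.

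A large age gap also makes the adjustment extrapolate from younger controls. Differences due to care setting or recruitment source remain.

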### **To evaluate the VOCs-based bronchiectasis detection mode**

Participants were recruited as mentioned above. The exhaled gas was collected and analysed as previously described. The data of 400 cases were randomly assigned in a 5:2:3 ratio to the discovery cohort, internal validation, and blinded test cohorts. The blinded test set was used for model evaluation.

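### The ten selected ions may include chance findings if few ions truly differ, because the last selection step is a rank and no ion is tested individually in held-out data

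*Combined protocol and SAP*

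**What the plan says.** The VOCs detection section states that "three hundred kinds of VOC ions features were extracted via breath detection in HPPI-TOFMS". The VOCs analysis section reduces these in three steps:

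1. It excludes "the breathomics features with no significant differences" between bronchiectasis and controls, at p > 0.05. No multiplicity adjustment is stated.
2. It removes low-intensity ions correlated above 0.9 with another selected ion.
3. It fits one random forest on the discovery data, and "the ten most important VOC ions were selected based on the feature coefficient in RF model". No minimum importance is given.

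The part of the Study plan on building the model adds: "The discovery and internal validation sets were used for potential VOC biomarkers selection and diagnostic model construction". The part on evaluating it says: "The blinded test set was used for model evaluation". The VOCs analysis section compares the model's results with the HRCT diagnosis in that set. The performance measures in the Statistical analysis section (sensitivity, specificity, accuracy, AUC) all describe the model. That section also lists Mann-Whitney tests between groups, but assigns none to single ions in held-out data.

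**The concern.** Selecting candidate biomarkers is one stated use of the data, alongside building the classifier. The classifier gets an independent check in the blinded set; the individual ions do not. The third step fixes how many ions are kept and uses importance only to order them. If the truly different ions run out before ten, the remaining places go to ions that passed a 0.05 screen by luck. A model carried by a few real ions can still perform well, so its AUC cannot show which of the ten are real. At stake is which ions the study may name as associated with bronchiectasis, not how well the model diagnoses it.

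**Working it through.** The plan contains no error-rate or sample-size calculation on this point, so there is no figure to reproduce.

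**Inputs from the documents.** There are 300 features. "A p-value<0.05 was considered statistically significant", and "All tests were two tailed". The plan has 200 patients and 200 healthy controls, split 5:2:3: 400 × 0.5 = 200 discovery, 400 × 0.2 = 80 internal validation, 400 × 0.3 = 120 blinded test.

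**Assumptions.** Each set is balanced (100 v 100 in discovery, 60 v 60 in the blinded set). Ions are normal and independent unless stated. The screen is a Mann-Whitney test run on development data only. Effect sizes are in SD units; the documents give none.

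**Step 1: the screen with no true ion.** Expected passes are 300 × 0.05 = 15. For X ~ Binomial(300, 0.05), P(X ≥ 10) = 0.935, so fewer than ten pass 6.5% of the time.

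**Step 2: the same with correlated ions (400 simulated data sets each).** The mean stays near 15, but P(at least ten pass) falls to 87%, 58% and 35% at a common correlation of 0.1, 0.3 and 0.5. In blocks of ten ions it is 92%, 78% and 69% at within-block correlation 0.3, 0.6 and 0.8. At 0.95 within blocks, the correlation filter leaves about 3 ions.

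**Step 3: a floor that needs no effect size.** If k ions truly differ and ten are kept, at least 10 − k are chance ions: 7 for k = 3, 5 for k = 5, 2 for k = 8, 0 for k ≥ 10. Enough null ions are available to fill the places: (300 − 3) × 0.05 = 14.85 and (300 − 5) × 0.05 = 14.75 are expected to pass.

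**Step 4: simulation of screen, then top ten (independent ions, 100 v 100).** Mean chance ions among the ten, ranked by forest importance or, as a check, by discovery p-value:

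| Real ions and effect | Forest ranking | p-value ranking |
|---|---|---|
| 3 at 0.8 SD | 7.0 | 7.0 |
| 5 at 0.6 SD | 5.4 | 5.2 |
| 10 at 0.6 SD | 1.4 to 1.6 | 1.1 |
| 20 at 0.6 SD | 0.1 or less | under 0.1 |
| 20 at 0.4 SD | 1.4 to 2.05 | 1.2 |

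The two rankings agree closely, so the result does not hinge on the forest.

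**Step 5: what the AUC shows.** With 3, 5 and 8 real ions at 0.8 SD, the mean blinded-set AUC was 0.77, 0.84 and 0.91, while about 7, 5 and 2 of the ten were chance ions. With no real ion it was 0.49.

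**Step 6: an ion-level test in the blinded set.** At the strictest Holm step, α = 0.05/10 = 0.005.
- If all ten were chance ions, 10 × 0.005 = 0.05 would be expected to pass at that level, and P(at least one) = 1 − 0.995^10 = 4.9%.
- By the normal approximation, power = Φ(d√(60/2) − 2.807). For d = 0.4, Φ(2.19 − 2.81) = 27%. For d = 0.6, Φ(3.29 − 2.81) = 68%. For d = 0.8, Φ(4.38 − 2.81) = 94%.
- In simulation with Holm over ten, 0.06 or fewer chance ions were kept on average. With 10 real ions at 0.6 SD, 6.2 of 8.6 selected real ions passed (loss 1 − 6.2/8.6 = 28%).
- With 5 real at 0.6 SD, 3.3 of 4.8 passed (loss 31%); one set of 60 runs gave 2.9 of 4.65 (loss 38%). A rerun of 1,000 data sets, ranked by p-value, gave losses of 25% with 10 real ions and 33% with 5.
- With 20 real at 0.4 SD, about 2.4 of 8.8 passed (loss 73%).

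**The case against.** The strongest reply is that selection here is mainly dimension reduction. The study's aim is diagnostic accuracy, the selection is introduced as a guard against over-fitting, and the word for the ions is already hedged. That stands, and it limits the point to what may be said about single ions.

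A reader might infer four stronger things that the documents do not support.

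- *That ten ions are returned whatever the evidence.* The p-value and correlation filters come first, and fewer than ten can survive (Steps 1 and 2).
- *That nothing removes false ions.* The screen discards about 95% of null ions, and ranking pushes weak ones down. The ten are also tested jointly: a wholly chance set would show an AUC near 0.5.
- *That the blinded-set accuracy is biased.* Noise inputs chosen without that set do not bias its sensitivity, specificity or AUC.
- *That an unstable list proves false ions.* Two simulated discovery draws from the same 400 people shared only about 4 of ten ions with 60 real ions, although almost none of those selected was noise. Many true ions were simply interchangeable.

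It is also fair to say that the problem nearly disappears if many ions differ clearly. The documents do not say whether they do, so the plan cannot rely on it.

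**Conclusion.** The point holds in a limited form. The plan selects candidate biomarkers with an uncorrected screen followed by a fixed-count rank, and it checks them only as a set. The size depends on an unknown, the number of ions that truly differ: more than half of the list could be noise if that number is 3 to 5, about one or two ions if it is 10 at 0.6 SD, and almost none if it is 20 or more at 0.6 SD. These figures rest on independent normal ions, assumed effects and a balanced split. With correlated ions and no signal, the ten places are filled less often than the 0.935 for independent ions.

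The diagnostic accuracy estimate stands, provided that selection used only development data, as the Study plan indicates. This is a worthwhile, cheap improvement to the biomarker claim and not a flaw in the main result.

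**What to change.** Add one paragraph to the VOCs analysis section and to the part of the Study plan on model evaluation:

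- Lock the ten ions, the direction of each difference and the model, and score the model on the blinded set first.
- Then test each ion in the blinded set against the same control group used for selection. Use a two-sided Mann-Whitney test, require the same direction as in discovery, and apply Holm over ten. The control group must be named, because the VOCs analysis section says only controls while the Study Population section includes both healthy participants and those with interstitial lung disease or sarcoidosis.
- Call an ion a confirmed candidate biomarker only if it passes. List the rest as *model inputs, not individually confirmed*, and state that this does not mean shown to be false.
- Bootstrap selection frequencies may be reported as description only, since a low frequency can also mean interchangeable true ions.
- State whether selection used discovery data alone or also internal validation data; the two sections differ. The blinded set lies outside both.

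The test needs no new data and leaves the accuracy estimate unchanged. The cost is lost true ions: at about 60 v 60, roughly a quarter to a third of selected real ions at 0.6 SD would go unconfirmed, and most at 0.4 SD. The report should say so beside the list.
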